Functional gastrointestinal disorders (FGID) affect 6-20% of the pediatric population however neither treatments nor pathophysiology are defined. In this age of the opioid epidemic, chronic pain and history of physical or psychological trauma are a well-known risk factor for substance use disorder¹⁹. FGID is currently considered to be a brain disorder with central sensitization. These 2 factors, chronic pain and history of trauma, are often present in FGID and other disorders with central sensitization²⁰⁻²³. Neuro-Inflammation plays an important role in the chronic pain of FGID^{24,25} and other central sensitization syndromes^{26,27}. These disorders often follow an infection or injury, with persistent low-grade systemic and mucosal inflammation after resolution of the original insult²⁸. A neuro-inflammatory cascade likely contributes to the eventual chronic pain state²⁴ through central sensitization and inhibition of the vagal anti-inflammatory pathway²⁹.

We and others have demonstrated that cardiovagal modulation measured by heart rate variability (HRV) is decreased in FGID and other chronic pain syndromes. Increasing vagal modulation either through cognitive behavioral therapy (CBT) or external auricular neuromodulation¹⁴ (manuscript in progress) decreases pain in children and adults with FGID. Another device, a cervical transcutaneous vagal stimulator, increased cardiovagal modulation and decreased production of TNF α^{30} . A parallel device, an ear microstimulator, appears to provide similar benefit, while stimulating only the auricular cutaneous territory of cranial nerve X (vagus). Evidence is mounting that these external auricular devices may be helpful in substance use disorder³¹. Substance use disorder is known to have an inflammatory substrate as well, as opioids are strong agonists at the TLR4 receptor³², and low doses of opioid antagonists such as naltrexone have strong anti-inflammatory effects³³. It is therefore possible that the impact of the auricular stimulator device in substance use disorder is also an anti-inflammatory mechanism.

We will compare the differences between 4 and 8 weeks of active auricular microstimulation by including a second phase in the study. This is will also ensure that all participants are guaranteed to receive active therapy even if they are assigned to the sham group in Phase I of the study. This will both aid in study recruitment, as well as giving us an additional comparator of sham and active therapies.

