D. DESIGN AND METHODS

We will enroll 30 subjects in this double-blind sham control study. Fifteen subjects will undergo sham stimulation for 4 weeks while the other 15 will have auricular microstimulation for 8 weeks. Then, the 15 subjects who were in the sham group will undergo stimulation for 4 weeks.

We will measure vagal modulation supine and standing utilizing heart rate variability, measure cytokines and mitochondrial bioenergetics through a Seahorse analysis at week 0, 4 and 8.

Inclusion Criteria:

- Female patients 12 18 years old with chronic idiopathic nausea, functional abdominal pain, dyspepsia and/or irritable bowel syndrome.
- English speaking

Exclusion Criteria:

- Patients who are unable to stand upright during the heart rate variability recording
- Patients with a known bleeding disorder
- Patients with swollen, infected, inflamed, or other skin eruptions on outer ear
- Patients with epilepsy
- Patients with any implanted cardiac pacemaker or defibrillator
- Patients with serious arterial circulatory problems in the lower limbs
- Patients with abdominal or inguinal hernia

- Patients who are pregnant
- Any unstable medical condition, such as renal disease, uncontrolled diabetes, etc.
- Requires new medication during the 8 weeks of the study that may affect the gastrointestinal symptoms, vagal modulation or immune response.
- Inability to answer questionnaires or report pain in a 0-10 visual analog scale.

Week 0 – Visit 1 (Enrollment)

A member of the research team will approach the patient and his/her legal guardian during his/her visit to the Functional and Gastrointestinal Disorders Clinic. If the patient and his/her guardian are unable to complete consent documents during the visit, the researcher may collect consent over the phone or at the study baseline visit in the Pediatric Translational Research Unit (TRU), prior to starting study procedures.

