Following the completion of consent, assent and HIPAA documents, a study physician will perform a brief medical assessment to confirm study eligibility. The "MD Assessment" form will be utilized for this assessment and will also collect demographic information such as birth dates, race and gender. Please see the form included with this project submission for complete list of data to be collected. Only patients who continue to meet study eligibility will be allowed to continue with this study. Participants will be advised that they are not allowed to start any new medications while participating in this study. If a new medication is needed, they should first notify the research team prior to starting the new medication. Vitals such as height, weight, BMI and blood pressures will be collected either during the patient's clinic visit or via chart review.

Heart rate variability will be collected using the FAROS 360 device. Electrode leads will be placed according to the diagram found in section F. The patient will be asked to lie supine in a dark, quiet room for 15 minutes and then asked to stand for an additional 5 minutes. A member of the research team or TRU nurse will be present during this recording to document if the patient moves or coughs. The patient will be allowed to sit or lie down if he/she is unable to stand for the entire time however, this will also be documented.

A member of the TRU who is qualified to perform phlebotomy will collect the blood samples for the analysis of cytokines and flow cytometry. Up to about 59ccs (3-4 tablespoons) will be collected. The blood samples will be escorted by a member of the research team to [name] lab (5th floor of the MACC Fund Building) where they will be prepared and frozen for later analysis by a member of the research team and/or by [name] laboratory technologist. A member of the research team will initiate the processing of these samples and transfer them to coded tubes before giving them to [name] lab.

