Study participants will complete the following study questionnaires: Functional Disability Inventory-Child and Adolescents Form, Symptom Intensity Questionnaire, Pain Catastrophizing Scale and Revised Child Anxiety and Depression Scale. The participant's parent will also complete the Functional Disability Inventory-Parent Form. The participant will also be asked to complete the TENS Unit Daily Recording Diary to document when the device was used. A member of the research team will review the questionnaire instructions with the study participants and will advise them that they are allowed to skip any question that they are not comfortable answering. The researcher will review the questionnaires for any missed responses and will confirm with the participant if the question(s) was intentionally skipped.

Subjects will be randomized to 2 groups: a) group 1: 15 females who will only undergo active auricular TENS unit stimulation for the 8 weeks. B) Group 2: 15 females who will undergo for the first 4 weeks sham (tactile) stimulation, and the 4 weeks of active stimulation. The active settings for the TENS unit is micro mode, pulse width: 50 millisecond (ms), a frequency of 10 Hertz (hz), and intensity at sub-sensory to minimally perceived threshold. The study investigating physician will place the first TENS unit to the participant's inner part of each ear (conchae) using a clip that is provided. The investigator will train the participant on how to place the unit at home. Subjects will be asked to use the unit for at least 1 hour, twice a day. The patient will determine what time during the day that they will utilize the unit, depending on their schedule. To document the placement and the time of day that the unit is use, a data collection form will be provided. A study team member's contact

information will also be provided if the patient has any questions or concerns. A study team member will contact the patient 2 times each month as a check in and reminder. The sham stimulation will be done with non-conductive cotton cushion applied to the electrodes and the TENS unit set at an intensity of 0.02mA. The investigator and performing research coordinator will be blinded to the stimulation mode. It is possible and permitted that the performing research coordinator will become aware of which group the subject is in when checking in on the subject.

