Participants will receive a \$20 check following the completion of each of the first study visit, a \$20 check after completing the second visit and \$30 for completing the final study visit. All checks will be written in the participant's name.

E. TOTAL NUMBER OF HUMAN RESEARCH PARTICIPANTS PROPOSED FOR THIS STUDY AT THIS SITE AND GLOBALLY. WHAT ARE THESE NUMBERS BASED ON?

For this pilot protocol, we will enroll 30 subjects from the Functional and Gastrointestinal Disorders Clinics in Children's Hospital of Wisconsin. The PI and her nurse practitioner see 16 patients with FGID per week. We have been performing many studies in our clinic and patients are usually very eager to participate; therefore, we are not concerned about the feasibility of completing this pilot study in 1 year. Furthermore, the study was designed so that every subject gets the active intervention, in part to increase enrollment and retention.

F. DRUGS OR PROCEDURES

MD Assessment Form

Investigating physicians will perform a brief medical assessment with the participant to confirm study eligibility. This assessment includes a detailed history of gastrointestinal symptoms such as nausea, vomiting, abdominal pain, location of pain, duration & frequency of symptoms, bowel movements – frequency and consistency. In addition, this form will be used to evaluate non-gastrointestinal comorbid burden such as abdominal migraine and cyclic vomiting syndrome, temporomandibular joint disorder (TMJ), chronic fatigue, urinary symptoms, pelvic pain (including dysmenorrhea, endometriosis etc.), other chronic pain types, Raynaud's syndrome, syncope, postural tachycardia syndrome, chronic nausea or vomiting, complex regional pain syndrome, panic disorder, PTSD, anxiety and affective disorders and fibromyalgia (original criteria), evaluated by assessing 18 tender points described by the American College of Rheumatology³⁴. Each symptom will be ranked as not present, possible, probable or definite based on the appropriate consensus criteria.

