Patients who turn 18 years of age while participating in this study will be re-consented either in clinic at a routine visit or over the phone. If a participant is re-consented over the phone, a member of the research team

will first mail the "Letter to Reconsent Enrolled Participants" and a blank Consent/HIPAA form to the participant's address listed in the participant's medical record. A member of the research team will call the participant to complete the informed consent discussion over the phone. Once the participant signs the Consent/HIPAA form, he/she will mail it back to the research team member who completed the discussion and he/she will complete the corresponding signature portion. A completed copy will be mailed to the participant and a copy will be uploaded into the participant's medical record. The researcher will document this process on the informed consent discussion form which will be filed with consent form.

O. PROCEDURES TO BE EMPLOYED IN ANALYZING DATA AND THE ANTICIPATED SIGNIFICANCE OF THE PROPOSED STUDY

Data Management and Analysis The data gathered will be entered into RedCap data system with each ID having a unique identifier for each participant. REDCap is a secure, web-based application for building and managing online databases. All data will be de-identified, and samples will only have a unique identifier that will link the unique identifier with the patient's name.

Missing Data: Every effort will be made to avoid missing data. Using logistic regression, the pattern of missing data will be explored. Assuming the data are missing at random (MAR) multiple imputations for items will be used.

Randomization: we will randomize using Piantadosi randomization in blocks of 10. The sample size in this pilot study is small and it would likely result in bad imbalance of the two groups.

Data analysis overview: Summary statistics, such as mean, median, standard deviation, range and correlation will be used as a first step to examine data. To satisfy parametric assumptions, we may perform transformations with justifications if possible and otherwise use non-parametric tests. Statistical software employed for data analysis will be: Cytel StatXact, SAS version 9.4, SPSS Version 24. The power calculation was made using PASS 15.

Heart Rate Variability

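### The new-medication exclusion covers the 8 weeks after randomisation, and the plan does not say what then happens to the participant's visits or data

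*Combined protocol and SAP*

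**What the plan says.** Section D, Exclusion Criteria, includes "Requires new medication during the 8 weeks of the study that may affect the gastrointestinal symptoms, vagal modulation or immune response". Randomisation takes place at week 0, so all of that window lies in follow-up.

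The Week 0 visit text in Section D adds an instruction, "Participants will be advised that they are not allowed to start any new medications while participating in this study", and a notice rule: "If a new medication is needed, they should first notify the research team prior to starting the new medication". It also plans regular contact: "A study team member will contact the patient 2 times each month as a check in and reminder". The instruction covers any new medication. The exclusion covers only those that could act on symptoms, vagal modulation or immunity.

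Section L names as stopping points a request from the family, failure to recruit, and unexpected adverse events. New medication is not among them.

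Section O defines no analysis set. On missing data it plans a logistic regression to explore the pattern, and then: "Assuming the data are missing at random (MAR) multiple imputations for items will be used". That sentence concerns items and does not address a participant who meets an exclusion after allocation.

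The randomised sham contrast covers weeks 0 to 4. Both arms are active in weeks 4 to 8, which serve a second aim in Section C: "We will compare the differences between 4 and 8 weeks of active auricular microstimulation by including a second phase in the study".

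**The concern.** A new medication already planned at week 0 can be screened for, but one that becomes necessary in week 3 cannot. If the criterion is applied to the second case, it is an exclusion made after randomisation on something that treatment may have influenced. New medication for gastrointestinal symptoms would plausibly follow poor symptoms, which are themselves an outcome.

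Three things are at stake:

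- **Numbers.** Each arm has 15 participants, so a few removals matter.
- **The week 4 contrast.** The window runs to week 8. A start in week 6 could lead to removal of a participant whose week 0 and week 4 data are complete and unaffected.
- **Discretion.** With no stated consequence, the decision could be made case by case after allocation. Section D allows the performing coordinator to learn the arm during check-ins, the same contacts at which a new medication could surface. Removal at different rates in the two arms is therefore conceivable.

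For hfHRV and cytokines there is a further difficulty. The criterion itself names drugs that may alter the measurement, so keeping the data without comment is not a complete answer either.

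**Working it through.** **No figure to reproduce.** Section O says that a power calculation was made, but the visible text gives no alpha, power, between-group difference or SD. What follows is illustrative.

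**Inputs.** From Section D: 15 per arm. Assumed: two-sided t-test at 5%, SD 1, true effect 0.8 SD, and the share needing new medication. The documents give no such rate, and the ban and check-ins may keep it low. Power under removal and retention was simulated.

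**1. Everyone analysed.** SE = √(2/15) = 0.365 SD, noncentrality 0.8/0.365 = 2.19, 28 df, power 56%.

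**2. Removal unrelated to outcome, 20% per arm.** This leaves 12 per arm. SE = √(2/12) = 0.408 SD, power 47%, no bias.

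**3. One need threshold in both arms.** Let Y be the outcome (higher is worse), sham N(0,1) and active N(−0.8,1). Need is M = ρY + noise, with variance 1 within arm. A participant is removed if M > c, where c = Φ⁻¹(1−p) and p is the sham share removed. With h(x) = φ(x)/Φ(x), the expected difference among those kept is

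0.8 − ρ[h(c) − h(c + 0.8ρ)].

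At p = 0.20, c = 0.842 and h(c) = 0.350. For ρ = 0.5, h(1.242) = 0.207, so the estimate is 0.8 − 0.5 × 0.143 = 0.728.

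| ρ (p = 0.20) | Active removed | Estimate (SD) | Power |
|---|---|---|---|
| 0.2 | 15.8% | 0.787 | 47% |
| 0.3 | 14.0% | 0.773 | 46% |
| 0.5 | 10.7% | 0.728 | 45% |
| 0.8 | 6.9% | 0.634 | 41% |

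Across the same range of ρ, removing 1 in 15 of sham gives 0.79 to 0.72 SD and power 53 to 50%. Removing one third gives 0.78 to 0.57 SD and 40 to 33%. With no true effect, this mechanism treats the arms alike: the difference is 0 and type I error about 5%.

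**4. Equal outcome-related removal.** With 20% removed in each arm and ρ = 0.7, the estimate stays at 0.80 SD and power goes only from 56% to 55%. Removing the worst outcomes also shrinks the within-arm SD. As ρ falls towards 0, this case becomes step 2.

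**5. Unequal outcome-related removal, no true effect.** With 10% removed in one arm and 30% in the other, h is 0.195 and 0.497. The bias is 0.7 × (0.497 − 0.195) = 0.21 SD. Its sign depends on which arm loses more, and type I error is about 8%.

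**6. Keeping everyone.** If the medication improves takers by b SD, the as-randomised estimate is 0.8 − b(p_sham − p_active). At p = 0.20 and ρ = 0.3, the difference in use is 0.200 − 0.140 = 0.060.

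- b = 1: 0.74 SD, power 50% (removal: 0.77 SD, 46%).
- b = 1.5: 0.8 − 1.5 × 0.060 = 0.71 SD, power 44% (removal: 46%).

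For hfHRV or cytokines, suppose 20% sham and 11% active use, with a drug that shifts takers by 1 SD. The contrast becomes 0.8 ± 0.09, that is 0.71 or 0.89 SD, against 0.80 to 0.76 SD under removal. In the worst of these cases as-randomised power is 42% against 49%.

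**The case against.** The strongest reply is that no section orders removal. The criterion sits in a list checked at week 0 and reads naturally as a judgement about expected need. Section L omits new medication from its stopping points. The Week 0 sentence making continuation depend on eligibility belongs to the enrolment check. Leaving the study is also not the same as leaving the dataset. All of this stands: removal is one reading, and a reader who infers that the protocol requires it goes beyond the text. What remains is that the wording permits that reading and nothing else settles it.

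A reader might also infer a contradiction with Section C, where "all participants are guaranteed to receive active therapy even if they are assigned to the sham group in Phase I of the study", and with Section E, where "the study was designed so that every subject gets the active intervention, in part to increase enrollment and retention". A sham participant removed before week 4 would indeed not reach active stimulation. But these lines describe the planned sequence for both arms, and any withdrawal, including one at the family's request, would have the same effect. They do not clearly contradict the criterion.

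Finally, this is a pilot of 30 with a medication ban, a notice rule and regular contact, so starts may be few. That limits the likely size but does not resolve the ambiguity.

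**Conclusion.** The point holds in a limited form and should be fixed. The exclusion reaches past randomisation, its consequence for visits and data is unstated, and the literal reading is a post-randomisation exclusion that could also discard sound week 4 data.

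The size is conditional. In the common-threshold illustration with 20% of sham removed, power drops from 56% to 41-47% and the estimate from 0.80 to 0.63-0.79 SD. All of this rests on an assumed effect, rate and mechanism.

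Three broader statements are tempting but unsupported:

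- **Removal always costs substantial power.** With equal outcome-related loss at correlation 0.7, the cost is about one point.
- **Bias is always towards no difference and vanishes under the null.** That needs one common threshold. Unequal outcome-related removal gives about 0.21 SD in either direction.
- **Keeping everyone always gives more power.** That fails in some settings once the new medication is worth about 1.5 SD to takers.

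The case for keeping all randomised participants rests on preserving the randomised comparison, not on a guaranteed gain in power.

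**What to change.** 1. Limit the criterion to facts known at or before randomisation, including a new medication already planned.
2. State that every randomised participant is measured at weeks 4 and 8 and analysed in her assigned arm, and that week 4 data are kept whatever happens later.
3. Record the date and type of any new medication at the existing twice-monthly contacts. Starts in weeks 0 to 4 bear on the sham contrast; those in weeks 4 to 8 bear only on the 4-versus-8-week comparison.
4. Report one supporting analysis, mainly for hfHRV and cytokines, that treats values after a relevant new medication as missing. Show it beside the as-randomised result. It would rest on missing at random, and the imputation in Section O would have to extend from items to whole visits.
5. Reconcile the exclusion list and the Week 0 text in Section D with Section L on what happens to the participant. No view is taken here on the medication rule or on whether she continues the device.

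The cost is a reworded criterion, a sentence or two on follow-up and analysis set, a short medication record and one extra analysis. The downside is that an effective new medication dilutes the as-randomised estimate, for example 0.74 SD against 0.77 SD under removal in step 6. With a benefit of about 1.5 SD or more in takers, the as-randomised analysis can also have less power than removal.

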The participant will be asked to contact the research team if they have any complications with the device or experience any adverse events.

Week 4 – Visit 2:

Study participants will return to the TRU to complete HRV and the study questionnaires specified in section F of the protocol. The participant's pain score and blood pressure will be obtained and documented on the MD Assessment Form. Participants who were randomized to receive sham therapy during weeks 0 to 4 will receive an active device. The study investigator will instruct these patients to turn it up until they feel it, then reduce the intensity until it just disappears. They will be asked to use the unit for a minimum of 1 hour, twice a day, until they return to CHW at Week 8 – Visit 3. The patient will determine what time during the day that they will utilize the unit, depending on their schedule. To document the placement and the time of day that the unit is use, a data collection form (diary) will be provided. A study team member's contact information will also be provided if the patient has any questions or concerns.

Participants who were randomized to receive active microstimulation at Week 0 - Visit 1, will continue to receive active microstimulation until they return at Week 8 – Visit 3.

A member of the TRU who is qualified to perform phlebotomy will collect the blood samples for the analysis of cytokines and flow cytometry. The participant's pain score and blood pressure will be obtained and documented on the MD Assessment Form. The coded blood samples will be escorted by a member of the research team to [name] lab where they will be prepared and frozen for later analysis by a member of the research team and/or by [name] laboratory technologist.

Week 8 – Visit 3:

Study participants will return to the TRU where they will complete HRV, the study questionnaires specified in section F of the protocol and a blood draw for cytokines and flow cytometry. The participant's pain score and blood pressure will be obtained and documented on the MD Assessment Form. The coded blood samples will be escorted by a member of the research team to [name] lab where they will be prepared and frozen for later analysis by a member of the research team or by [name] laboratory technologist.

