Blinding methodology: Patients will be informed that we are comparing 2 methods of ear stimulation, tactile and active. Both methods will be explained (either setting the machine at 0.02mA and using dry, nonconductive pads, or moving the device up until the stimulus is just experienced and then lowering until it is no longer experienced). Because the first stimulus is tactile, we will not use the word "sham" or "placebo", as we do not know that a tactile stimulus does not have some effect. In fact, ear piercings are popular for these symptoms. After both methods are explained the subject will demonstrate understanding of each. Once home, the patient will open a sealed envelope that was prepared by an independent research coordinator, and unknown to the investigator or the performing research coordinator, that instructs them as to which method to utilize. Only the independent research coordinator and the biostatistician will know the arm assigned. At the participant's Week 4 visit, the researcher will collect the previously used TENS unit device. The research coordinator will then provide all participants with another auricular device and letter which will include instructions on how to use the device during the remaining 4 weeks. It is remotely possible that some subjects will realize that the tactile form of the stimulation with dry cotton pads is actually a **sham** version of the stimulator. We think this is unlikely for 2 reasons. First, tactile stimulation of the ear is in fact sometimes referenced in the popular literature as a treatment (though this has not been formally tested). Second, neither version of the stimulator produces any conscious electrical sensation, so they will be quite comparable from an experiential perspective. In addition, the fact that tactile stimulation may have some effect will not alter the fundamental goal of this protocol, as we will be looking at the difference between the tactile and the electrical stimulating version. It is possible and permitted that the participant and the research team will become aware of which group the participant was initially assigned at the Week 4 visit.

TENS unit and Auricular Clip Placement

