The TENS unit and auricular clip will first be placed by a qualified study investigator (physician) who will also provide teaching to the participant and family on how to place it at home. TENS unit applied to the inner part of each ear (conchae) by a qualified study investigator using a clip that is provided. The active settings will be set to the following: Micro mode, pulse width: 50 millisecond (ms), a frequency of 10 Hertz (hz), and intensity at sub-sensory threshold. This is the same process used for standard of care.

small intestine point heart point

A

R

the distribution areas of, ABVN in the external ear.

Heart rate variability (HRV) using the Faros ECG 360

The Faros ECG 360 is a remote electrocardiography monitoring system that is used for real-time HRV measurements. The ECG data will be transmitted from 3-5 electrodes (stickers) placed on the body (pictured below) to a mobile device through Bluetooth. The data can be retrieved in two ways: through a web browser for analyzing or with real time monitoring view on a computer. A password protected laptop will be used to import the data and then to import it into an HRV analysis software.

Heart rate variability will be collected using the FAROS 360 device. Electrode leads will be placed according to the diagram found in section F. The patient will be asked to lie supine in a dark, quiet room for 15 minutes and then asked to stand for an additional 5 minutes. A member of the research team or TRU nurse will be present during this recording to document if the patient moves or coughs. The patient will be allowed to sit or lie down if he/she is unable to stand for the entire time however, this will also be documented.

Questionnaires to be completed for research purposes

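### Active stimulation intensity is stated inconsistently between sections, and the upper end of the Week 0 range contradicts the no-sensation premise of the blinding argument

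*Combined protocol and SAP*

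**What the plan says.** The protocol states the active intensity in four places.

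- Section D, Week 0 visit: after describing both groups, the text gives the active settings once, with "intensity at sub-sensory to minimally perceived threshold".
- Section D, Week 4 visit: participants coming off sham are told to "turn it up until they feel it, then reduce the intensity until it just disappears".
- Section F, blinding methodology: the active method is explained as "moving the device up until the stimulus is just experienced and then lowering until it is no longer experienced". This goes to everyone: "After both methods are explained the subject will demonstrate understanding of each".
- Section F, TENS unit and clip placement: "intensity at sub-sensory threshold".

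The sham is a non-conductive cotton cushion with "the TENS unit set at an intensity of 0.02mA".

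The blinding text gives two reasons for thinking that participants are unlikely to see the tactile version as a sham. One is that touch stimulation of the ear is sometimes mentioned in popular literature as a treatment. The other is that "neither version of the stimulator produces any conscious electrical sensation".

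Section C adds a second aim for the extension phase: "We will compare the differences between 4 and 8 weeks of active auricular microstimulation". It does not define the contrast.

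**The concern.** A range that runs up to a felt stimulus and a statement that no stimulus is felt cannot both describe the same active arm. The sham contrast in weeks 0-4 depends on the two versions being alike to the user. Clinical improvement is measured by the Functional Disability Inventory and by symptom ratings, which participants (and, for the inventory, also parents) report themselves. Section A says that the placebo effect in these disorders is high and treats a blinded sham arm as critical. If some active users feel current and no sham user does, expectation may differ between arms on exactly those outcomes.

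The wording matters in practice because participants apply the assigned method themselves at home, after opening the envelope. The protocol describes no record of the active setting. The diary has columns for the date and two times of use, and the visit text asks for placement and time of day. It could not be shown afterwards which definition was followed.

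**Working it through.** No arithmetic applies: the plan gives no figure on this point, and the documents contain no data linking intensity to outcome. The check is a side-by-side reading.

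| Place | Whom it addresses | Where the intensity ends |
|---|---|---|
| Section D, Week 0 visit | Active settings in general, stated after both groups are named | Anywhere from below perception to just felt |
| Section D, Week 4 visit | Sham participants switching to active | Below perception, after raising and lowering |
| Section F, blinding methodology | Every participant, before allocation is known to her | Below perception, after raising and lowering |
| Section F, clip placement | Active settings in general | Below perception |

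**Step 1: consistency.** Three of the four statements end below perception. One, the Week 0 text, permits a felt level. The four are not equivalent.

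**Step 2: against the blinding premise.** A participant who follows the three narrower statements has no sensation once the unit is set. One who uses the upper end of the Week 0 range does, and the no-sensation sentence is then untrue for her. A smaller tension remains under any raise-then-lower rule: the active user feels the stimulus briefly at set-up, so the sentence is not literally exact even then.

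**Step 3: who can be affected.** The blinded contrast covers weeks 0-4, when only the 15 participants of Group 1 use active stimulation. That is an upper bound on the number exposed, not an estimate. From the Week 4 visit the protocol accepts that participants and staff may learn the initial assignment.

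**Step 4: is the conflict tied to group?** No. The Week 0 text describes active settings after naming both groups, including Group 2's later active period. The method explained to every participant is in substance the one given to Group 2 at Week 4. The only asymmetry is that the Week 4 text records an investigator's instruction for former sham participants alone, while Group 1 simply continues. Section F says that everyone then receives another device and an instruction letter, whose content is not given.

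**Step 5: what duration confounding would need.** Two things: (a) Group 1 using the wider range while Group 2 uses the narrower rule, and (b) a between-group contrast, such as Group 1 after 8 weeks of active use against Group 2 after 4. A comparison of Week 4 with Week 8 within Group 1 would carry no between-group difference in intensity, although a change of setting over time could still enter it. Section C does not say which contrast is meant.

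**The case against.** The strongest reply is that this is a loose phrase and not a design fault. Every participant is taught to raise and then lower until nothing is felt, the placement text agrees, and a reasonable reader would take that as the operative rule. Much of this stands: the conflict lies between sections, and the prevailing description agrees with the blinding text once the unit is set. But the Week 0 paragraph is the operative description of the active settings, and someone following it could use a felt level without deviating from the protocol.

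A second reply is that the envelope already tells each participant which method she is using, so a faint sensation adds little to what she knows. That is fair as far as knowledge of the method goes. The protocol's argument, however, is that the two methods are alike in experience, so that neither seems the lesser treatment. Sensation bears directly on that.

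A reader might infer more: that the two groups are assigned different active intensities, that the comparison of 4 with 8 weeks is therefore confounded in all 30 participants, or that the blinding fails. The documents support none of these. Steps 4 and 5 show why the first two do not follow. As to the third, only the upper end of one range conflicts with the no-sensation sentence, and that sentence is one of two reasons offered.

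**Conclusion.** The point holds as an inconsistency between sections with a consequence for the blinding rationale. One of four statements of active intensity permits a felt stimulus and so contradicts a stated premise of the sham comparison. Up to 15 participants could be affected in weeks 0-4; how many would actually use a felt level is unknown, and no effect in outcome units can be derived.

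Confounding of intensity with duration is a conditional risk only. It rests on two assumptions that the documents neither confirm nor exclude: uneven application of the wordings, and a between-group contrast. It is a further reason to settle on one definition, not a defect already present.

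The matter is worth correcting because the key clinical outcomes are self-reported, the protocol itself stresses the placebo response, and the correction is small.

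**What to change.** Reconcile the Week 0 and Week 4 visit texts in Section D with the blinding and clip-placement texts in Section F, so that one intensity definition applies to all active use, in both groups and both periods, and agrees with the blinding statement. Which wording is right is for the sponsor. The Week 4 letter should carry the same definition.

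Optionally, add the setting used to the participant's existing device diary. Two cautions apply.

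- The method is revealed at home after the Week 0 visit, so an entry made by staff at that visit would miss the setting actually used. A 0.02 mA entry would also reveal the sham arm. Entries for weeks 0-4 should therefore go only to the independent coordinator, who already knows the allocation.
- Intensity is set to each person's own threshold, so mA will vary by design. The entries document adherence to the definition; they do not show equal mA between groups, and equality should not be the test.

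The cost is a wording amendment and, if the option is taken, one diary column and controlled handling of the diary. Sample size, visits and assessments do not change.
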